9.0 STATISTICAL CONSIDERATIONS

9.1 General Considerations

The comprehensive SAP with detailed description of all statistical analyses will be developed and finalized before database lock.

All statistical analyses, including summary tables and data listings will be performed using SAS[®] software (version 9.4 or higher). Continuous endpoints will be summarized using descriptive statistics (number of subjects [n], mean, standard deviation [SD], median, minimum, and maximum). Categorical endpoints will be summarized using frequency counts and percentages. All individual subject data will be present in listings.

9.2 Sample Size Determination

[REDACTED]

- | [REDACTED]
- | [REDACTED]
- | [REDACTED]
- | [REDACTED]

Based on the assumptions above and using a two-sample t-test, a sample size of 60 subjects per treatment group is needed to detect the treatment effect on the primary endpoint between RPT193 and placebo. Assuming a 10% drop out rate, a total sample size of approximately 265 subjects (approximately 67 per treatment group) will be needed.

9.3 Populations for Analyses

For purposes of analysis, the analysis sets in [Table 5](#) are defined.

Table 5 Analysis Sets

Analysis Set	Description
Full Analysis Set (FAS)	All subjects who have been randomized to a study treatment group. FAS will be the primary analysis set for all efficacy analyses. Subjects will be analyzed according to their randomized treatment.
Per-Protocol (PP) Analysis Set	All subjects in FAS with no major protocol deviation that would have an impact on the primary and key secondary efficacy assessments. Major protocol deviations will be reviewed and determined prior to database lock. Subjects to be excluded from the PP analysis set will be determined based on a blinded data review meeting prior to database lock. Subjects will be analyzed according to their randomized treatment.
Safety Analysis Set	All randomized subjects who receive at least 1 dose of study treatment. This analysis set will be used for all safety analyses. Subjects will be analyzed according to the treatment they received.

9.4 Statistical Analyses

9.4.1 Subject Disposition and Demographics

Subject disposition events as well as the number of subjects in each analysis sets will be summarized using frequency counts and percentages by treatment arms.

Demographic and baseline characteristic will be summarized as appropriate.

9.4.2 Primary Efficacy Analysis

The primary efficacy endpoint is the percent change from baseline in EASI score at Week 16.

The primary estimand is defined as

- Population of interest: adult subjects with moderate-to-severe AD as defined by the inclusion/exclusion criteria
- Variable/endpoint of interest: percent change from baseline in EASI score at Week 16.
- Intercurrent event handling strategy:
 - Early termination of study treatment: subjects who discontinue from the study treatment prior to Week 16 will be analyzed by the treatment policy strategy, i.e., all data collected will be included in analysis.
 - Use of rescue medications: subjects who use rescue medication during the 16-week treatment period will be analyzed by the hypothetical strategy. All EASI scores collected after the start of rescue medication will be set to missing and imputed.
- Population-level summary measure: difference in mean percent change from baseline in EASI score between RPT193 and placebo.

The primary analysis will be performed in FAS. The primary efficacy endpoint will be analyzed with ANCOVA model. The model will include treatment group (each RPT193 dose vs. placebo), baseline vIGA scores, randomization stratification factors and study sites as factor, and baseline EASI score as a covariate. The least square (LS) mean and LS mean difference along with the 95% confidence interval (CI) and p-value will be reported.

The following sensitivity analysis will be planned for the primary estimand:

- In FAS, including only the observed data regardless of rescue medication uses and without missing data imputation.
- In PP analysis set, following the same model as described for the primary estimand.

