7.0 DISCONTINUATION OF STUDY TREATMENT AND SUBJECT DISCONTINUATION/WITHDRAWAL

7.1 Discontinuation of Study Treatment

See the SoA for data to be collected at the time of Early Termination/Treatment Discontinuation and follow-up and for any further evaluations that need to be completed.

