7.2.1 Discontinuation

Subjects who discontinue the study after the first dose will be asked, if they agree, to come for a last assessment (ET/Discon visit). Subjects who are discontinued for safety reasons may be asked to come for additional follow-up visits, at the Investigator's discretion, after the ET/Discon visit to ensure appropriate medical care and AE follow-up.

Reasons for discontinuation include the following:

- The Investigator decides that the subject should be withdrawn for any of the following reasons, but not limited to: difficulties in obtaining blood samples, violation of the protocol, severe AEs or SAEs, or for any other reason relating to the subject's safety or integrity of the study data. If this decision is made because of a SAE, the study drug is to be discontinued in that subject immediately and appropriate measures are to be taken. The Investigator will notify the Sponsor immediately.
- The attending physician requests that the subject be withdrawn from the study.
- The subject, for any reason, requires treatment with another systemic therapeutic agent that has been demonstrated to be effective for treatment of the study indication (e.g., oral corticosteroids, dupilumab, tralokinumab oral calcineurin inhibitor, oral immunosuppressive). In this case, discontinuation from the study occurs immediately upon introduction of the new agent.
- The subject is lost to follow-up. In this case, a reasonable attempt to contact the subject and ascertain his or her status must be made, and these attempts must be documented.
- The subject becomes pregnant at any time during the study.
- A clinically significant change in a laboratory parameter occurs (See [Table 4](#)),
- Onset of an opportunistic infection during the study.
- Other: the subject may withdraw from the study for any other reason, including withdrawal of consent.

- The Sponsor or regulatory authorities, for any reason, stop the study. In this case, all subjects will be discontinued from the study. The Investigator will immediately, on discontinuance of the study by the Sponsor, in its entirety or at a clinical trial site, inform both the subjects and the Institutional Review Board/Research Ethics Board/Independent Ethics Committee (IRB/REB/IEC) of the discontinuance, provide them with the reasons for the discontinuance and advise them in writing of any potential risks to the health of subjects or other persons.

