- If during the course of treatment, a subject experiences a new onset cardiovascular adverse event consistent with Common Terminology Criteria for Adverse Events (CTCAE) Version 5.0 of Grade ≥ 2 , such subjects should be discontinued from further dosing and, if applicable, followed for resolution.
- If a subject experiences a new onset adverse hematologic adverse event (including laboratory abnormalities) of Grade ≥ 2 , such subjects should first have laboratory abnormalities verified by repeat measure, and if repeat measure confirms the new onset abnormality, such subjects should be discontinued from further dosing, and if applicable, followed for resolution.
- If a subject experiences an adverse event Grade ≥ 3 for any organ system, such subjects should be discontinued from further dosing and, if applicable, followed for resolution.
- The study drug should be discontinued in subjects who develop evidence of hepatocellular injury that may be caused by the study drug consistent with Hy's Law. Such an adverse event should be reported as a serious adverse event (SAE).

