### A. Estimand

The main estimands associated with the primary and key secondary endpoints to support regulatory decisions are described in the following table:

Attribute	Description
Treatment	RPT 193-02 (50mg, 200mg, 400mg) and Placebo
Population	Adult subjects with moderate-to-severe AD as defined by the inclusion/exclusion criteria
Endpoint	
Primary Endpoint
 
 
% change in Eczema Area Severity Index (EASI) from baseline at Week 16
 
 
Key Secondary Endpoints
 
 
% of subjects achieving a Validated Investigator Global Assessment (vIGA) score of 0 or 1 at Week 16
 
% of subjects achieving EASI-75, defined as a 75% reduction in EASI from baseline to Week 16
 
% change from baseline in PP-NRS from an itch daily e-Diary at Week 16.
 

Intercurrent Events	
 
Early termination of study treatment: Subjects who discontinue from the study treatment prior to Week 16 will be analyzed by the treatment policy strategy, i.e., all data collected after termination of study treatment but prior to rescue medication will be included in the analysis. Missing post discontinuation values will be imputed according to details provided below.
 
Use of rescue medications: Subjects who use rescue medication during the 16-week treatment period will be analyzed by the hypothetical strategy. All EASI/vIGA/PP-NRS scores collected after the start of rescue medication will be set to missing. The missing data after the use of rescue medication will be imputed to follow a similar profile as the placebo group.
 

Population-level Summary	
Primary Endpoint
 
 
Difference in mean percent change from baseline in EASI score between each RPT193 dose and placebo at Week 16.
 
 
Key Secondary Endpoints
 
 
Difference in percentage of subject achieving vIGA of 0 or 1 between each RPT193 dose and placebo at Week 16.
 
Difference in percentage of subject achieving EASI-75 between each RPT193 dose and placebo at Week 16.
 
Difference in mean percent change from baseline in PP-NRS
 

	between each RPT193 dose and placebo at Week 16.
--	--

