#### **Control-based PMM-MI procedures for EASI, PP-NRS, and vIGA under MNAR**

Similar to MI under MAR, but for EASI, PP-NRS, and vIGA, data collected after the intercurrent events of rescue medication or treatment discontinuation in the RPT193 arm will be assumed missing not at random (MNAR) and resemble missing data from subjects from the placebo arm who do not discontinue treatment permanently/receive rescue medication. Imputation of missing data at Week 16 will be done using a control-based Pattern Mixture Model Multiple Imputation (PMM-IM) where missing data in the study drug (RPT-193) arm as well as the placebo arm will be imputed from observed data in the placebo arm.

The intermittent missing data will be imputed separately for each treatment group using the Markov Chain Monte Carlo (MCMC) method implemented with the SAS PROC MI procedure. 100 imputed datasets will be generated.

For each of the 100 datasets a monotone missing data pattern will be achieved. The monotone missing values will then be imputed from subjects in the placebo group using the SAS PROC MI procedure with MNAR statement. This assumes that the missing data will follow a similar profile as the placebo group.

After the completion of the imputation, the assessments collected after the discontinuation of study treatment yet before to the use of rescue medication will be restored. The example code can be found in Appendix II.

The categorical secondary endpoints will be derived from the imputed scores in each MI datasets.

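### The primary and key secondary estimands apply a treatment-policy strategy to stopping study drug, but the protocol does not provide for Week 16 efficacy data from subjects who stop

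*Protocol*

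**What the plan says.** **The estimand.** Under Protocol 9.4.2, subjects who stop study treatment before Week 16 "will be analyzed by the treatment policy strategy, i.e., all data collected will be included in analysis". The SAP (II.A, Estimand) applies the same strategy to the primary and key secondary endpoints, limits it to data before rescue, and adds: "Missing post discontinuation values will be imputed according to details provided below".

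**Data collection after stopping.**
- Protocol 7.1, on stopping treatment, sets no visit rule of its own: "See the SoA for data to be collected at the time of Early Termination/Treatment Discontinuation and follow-up". The Schedule of Activities (1.3) has one discontinuation column, shared with Day 127 (Week 18).
- Protocol 7.2.1: "Subjects who discontinue the study after the first dose will be asked, if they agree, to come for a last assessment (ET/Discon visit". Those stopped for safety reasons "may be asked to come for additional follow-up visits, at the Investigator's discretion, after the ET/Discon visit", for medical care and adverse-event follow-up.
- The dose-stopping rules are in the same section, under 7.2 on withdrawal from the study. The rule for events of Grade 3 or higher, for example, reads "such subjects should be discontinued from further dosing and, if applicable, followed for resolution".
- Footnote j of the schedule has the e-Diary collected or removed at end of study or at ET/Discon.

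**Analysis.** The SAP (IV.D.2) imputes missing values from a model fitted to the placebo arm. Afterwards, "the assessments collected after the discontinuation of study treatment yet before to the use of rescue medication will be restored".

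**The concern.** A treatment-policy estimand asks what happened at Week 16 whether or not the subject was still taking drug. It can be estimated without modelling only if those who stop are still assessed at Week 16. Here the estimand calls for such data, but the visit rules contain no instruction to obtain them. The SAP's restoring step puts off-drug values back only if someone collected them.

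Where they were not collected, the Week 16 value comes from placebo-arm behaviour. For those subjects the estimate is reference-based, although it carries a treatment-policy label, and it rests on an assumption that the trial's own data cannot test. This matters more than usual here, because the protocol's rationale (2.1) is that benefit may outlast dosing. Off-drug outcomes are therefore of direct interest.

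**Working it through.** **1. The plan's own figure.** Inputs: 60 evaluable per group, 10% dropout, four groups (Protocol 9.2, SAP III.C). 60 / (1 − 0.10) = 66.7, rounded up to 67; 67 × 4 = 268. This matches the SAP exactly, and the protocol's figure of about 265 is close. The 60 itself cannot be checked because its inputs are redacted, so no statement about power is made here.

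**2. What the estimand needs against what is scheduled.**

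| Needed from a subject who stops drug | Provision found |
|---|---|
| EASI and vIGA at Day 113 | No instruction to attend. 7.1 points to the schedule, which offers only Day 127/ET/Discon for discontinuation |
| Daily itch score up to Day 113 | Diary collected or removed at ET/Discon |
| Staying in the study | Stated in 6.6.4 for subjects rescued between Day 57 and Day 113. No matching sentence for those who stop drug |
| Contact after ET/Discon | Optional visits for safety cases. Adverse-event collection ends 28 days after last dose for early terminators (8.3.1) |

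The third row is the most telling. The protocol keeps rescued subjects on schedule, although their later scores are set to missing for the estimand. It says nothing of the kind for those who stop drug, whose later scores the estimand uses.

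**3. When an ET/Discon assessment counts as Week 16.** The SAP (IV.C) assigns EASI and vIGA by actual study day, and the Week 16 window is Days 99 to 119. An ET/Discon EASI on Day 60, for example, falls in the Week 8 window (Days 43 to 70). For itch, Week 16 is Days 107 to 113 with at least three entries, so the diary must be in use until at least Day 109 (107, 108, 109).

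**4. How many subjects.** 268 × 0.10 = 26.8, about 27 in total. That is 6.7 in each arm of 67, so about 20 on active drug (201 × 0.10 = 20.1) and about 7 on placebo. This is an illustration, not an estimate:
- The 10% is failure to complete the study (5.5), and completion runs to Week 24 (4.4). Subjects who leave after Day 113 already have a Week 16 value.
- Subjects who withdraw consent or are lost would not be recovered by scheduling visits.
- Subjects withdrawn for needing topical therapy before Day 57 (6.6.4) would gain little, because post-rescue values are set to missing anyway, if that therapy counts as rescue.
- No document gives the rate of stopping drug before Week 16.

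**5. Why the bias cannot be sized.** Let Δ be the full on-drug effect and m the share of the active arm that stops drug and has no Week 16 value. Let f be the fraction of Δ that these subjects truly keep, and g the fraction that the imputation gives them.

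- Treatment-policy target: Δ[(1 − m) + m·f]
- Estimate: Δ[(1 − m) + m·g]
- Shortfall: m·Δ·(f − g)

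With m = 0.10 and g = 0 (both assumed), f = 0.25 gives 0.025Δ, f = 0.50 gives 0.05Δ and f = 1 gives 0.10Δ. However, g need not be zero. The code in SAP Appendix II regresses Week 16 on the subject's own baseline and Weeks 2 to 12, so earlier benefit is partly carried forward. If g exceeds f, the sign reverses. The documents give none of m, f and g.

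**The case against.** The strongest reply is that the text does not clearly send those who stop drug out of the study. The last-assessment sentence in 7.2.1 refers to leaving the study. The dose-stopping rules speak of further dosing. Section 7.1 treats stopping treatment separately and mentions follow-up. SAP V.A counts the two kinds of discontinuation separately, and the restoring step presupposes off-drug data. A site could keep these subjects on schedule.

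This stands as far as it goes. A reader might infer that Week 16 outcomes are mostly uncollected, or that nearly all who stop are imputed. The documents give no such share, so that reading is not supported. What remains is that nothing tells a site to continue the visits.

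A reader might also infer that the effect is diluted by 10% or more. That would take study dropout for stopping drug, set every imputed active subject to the placebo mean, and assume full benefit off drug. None of these follows from the documents. Nor does the rationale of persisting benefit fix the direction: Protocol 2.2.2.6 reports improvement up to two weeks after a four-week course, and 2.2.2.4 a half-life of about 24 hours. Neither shows benefit lasting from an early stop to Week 16.

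Finally, the SAP is open about the imputation and varies the assumption (MAR imputation, MMRM, LOCF, WOCF, observed cases). These analyses show sensitivity to the assumption, but none supplies the missing outcomes.

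**Conclusion.** The mismatch holds. Both documents name a treatment-policy strategy for stopping drug before Week 16, and the protocol does not provide for the Week 16 efficacy data that it needs. For subjects whose ET/Discon visit falls before Day 99, there may be no Week 16 EASI or vIGA to restore, and the result then rests on placebo-based imputation. The gap is clearest for the itch score, because the diary is taken back.

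Its size is unknown. About 27 of 268 is study dropout through Week 24; it includes placebo subjects and losses that no visit rule would recover. The conclusion rests on the absence of an instruction, read across 7.1, 7.2.1, the schedule and 9.4.2, and not on any assumed discontinuation rate. This is a cheap improvement. It does not make the primary analysis invalid.

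**What to change.** **Protocol.** Reconcile 7.1, 7.2.1 and the Schedule of Activities with 9.4.2. State that subjects who stop study drug but do not withdraw consent continue the already scheduled EASI, vIGA and itch-diary assessments through Week 16, and keep the e-Diary until then. These visits are in addition to the ET/Discon assessments, which 7.1 assigns to treatment discontinuation and which include fasting laboratory tests; they should not replace them. No stopping, dosing or rescue rule changes.

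**SAP.** Report observed versus imputed Week 16 values by arm and by reason. If visits can no longer be added, describe the estimate as reference-based for subjects who stopped drug and were not observed at Week 16. The SAP allows modification until unblinding (I.B).

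**Cost.** Some protocol wording, one extra table, and slight extra visit and diary burden for a small group.

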9.4.2.1 Secondary Efficacy Analysis

For continuous secondary endpoints, the same model as discussed for the primary analyses will be followed. For binary secondary endpoints, a logistic regression model with treatment group, baseline vIGA scores, randomization stratification factors, study sites as factors and baseline score as a covariate will be used.

9.4.2.2 Multiplicity

For the primary efficacy endpoint, to preserve the Type I error at 0.05, a serial gatekeeping strategy will be employed to address the multiplicity of the pairwise comparison of each RPT193 dose vs. placebo. The order of the testing will be performed from the highest RPT193 dose to the lowest dose. Testing will stop if non-significance (2-sided p-value ≥ 0.05) is observed.

9.4.3 Safety Analyses

All safety analyses will be performed on the Safety Analysis Set.

Adverse events will be coded using the Medical Dictionary for Regulatory Activities (MedDRA). A TEAE is any condition that was not present prior to treatment with the study drug but appeared following treatment, was present at treatment initiation but worsened during treatment, or was present at treatment initiation but resolved and then reappeared while the individual was on treatment (regardless of the intensity of the AE when the treatment was initiated).

The AE summaries will be primarily based on TEAEs. Descriptive statistics for the number and percentage of subjects with TEAEs will be summarized by treatment arm, system organ class, and preferred term for all TEAEs, treatment-related TEAEs, serious TEAEs, and TEAEs leading to discontinuation of study treatment. All TEAEs will be further summarized by maximum severity and causality.

All AEs will be present in a by-subject listing. Serious AEs, and TEAEs leading to discontinuation of study treatment will be present in separate listings.

Adverse Events of Clinical Interest

A separate analysis focused on the following events of clinical interest will also be performed: malignancy, major adverse cardiac events (MACE), tuberculosis (TB), inflammatory bowel disease (IBD), depression and suicidal ideation and behavior, serious or opportunistic infection (e.g., infection resulting in hospitalization, requiring IV antibiotics, or considered life-threatening), and hypersensitivity reactions.

Clinical Laboratory Tests

Laboratory data will be summarized using descriptive statistics for each parameter, including change baseline at each assessment time by treatment arm. Frequency tables or shift tables will be used to present the number and percentages of subjects with laboratory values within/outside normal reference ranges. All laboratory data will be present in the listings. A by-subjects listing will also be provided for subjects with abnormal laboratory results.

12-Lead Electrocardiogram (ECG) and Vital Signs

Descriptive statistics will be used to summarize the observed and change from baseline values of the ECG and vital signs parameters at each assessment time point by treatment group. All ECG and vital signs data will be present in listings.

9.4.4 Other Analyses

Pharmacokinetic (PK), pharmacodynamic, exploratory endpoints and skin microbiome analyses will be summarized using descriptive statistics and will be listed and summarized in a tabular and/or graphical form.

9.4.5 Missing Data

For the primary and key secondary efficacy endpoints, the efficacy data collected after the start of rescue medication will be set to missing. All missing data up to Week 16 will be imputed using a multiple imputation (MI) technique as follows:

- Intermittent missing data will first be imputed using the Markov Chain Monte Carlo (MCMC) method implemented with the SAS PROC MI procedure and imputed datasets with monotone missing pattern will be generated. This applies to intermittent missing data prior to the intercurrent events including early termination of the study treatment as well as initiation of rescue medications.
- The monotone missing values will then be imputed with the imputation model estimated from subjects in the placebo group using the SAS PROC MI procedure with MNAR statement. This approach is based on the missing not at random (MNAR) assumption. This assumes that the missing data in

the RPT193 doses post treatment discontinuation and/or the start of rescue medication follow similar profile as the placebo group.

- Response status (Yes, No) will be derived from the imputed scores in each MI datasets for binary endpoints. The results of the multiple MI datasets will then be combined into a single analysis using PROC MIANALYZE.

As a sensitivity analysis, all missing continuous data up to Week 16 will also be imputed by using last observation carried forward (LOCF). Missing data for responder endpoints will be imputed as treatment failures (TF). Additional sensitivity analyses under different assumptions for missing data handling may be explored in the SAP.

